### 10.2.2.11 Time to Discontinuation to Treatment

Kaplan-Meier estimates of the percentage of subjects completing 3, 6, 12, 18, and 24 months of treatment will be provided for the SS. For subjects who discontinued from the study, the event date is set to the date of last dose of PSL and the time to event will be calculated as the date of

last dose minus the date of first dose of PSL in EP0093 plus 1. Subjects who completed the study will be censored as of the date of last dose of PSL in EP0093. At a clinical cutoff, subjects who are ongoing will be censored as of the date of last dose of PSL defined for the interim analyses (Section 3.2.2.1).

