11.4 Termination of the study

UCB reserves the right to temporarily suspend or prematurely discontinue this study either at a single site, multiple sites, or at all sites at any time for reasons including, but not limited to, safety or ethical issues, inaccurate or incomplete data recording, noncompliance, or unsatisfactory enrollment with respect to quality or quantity.

If the study is prematurely terminated or suspended, UCB (or its representative) will inform the Investigators/Institutions and the regulatory authority(ies) of the termination or suspension and the reason(s) for the termination or suspension, in accordance with applicable regulatory requirement(s). The IRB/IEC should also be informed and provided with reason(s) for the termination or suspension by the Sponsor or by the Investigator/Institution, as specified by the applicable regulatory requirement(s). In addition, arrangements will be made for the return of all unused PSL and other material in accordance with UCB procedures for the study.

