## 1 INTRODUCTION

This statistical analysis plan (SAP) defines the scope of statistical analyses and provides a detailed description of statistical methodology for the statistical analyses to support the final

clinical study report (CSR). The SAP is based on the following study document: Protocol EP0093 Amendment 2, 4 February 2020. All references to study protocol hereafter refer to this version of the protocol. Unless otherwise specified, the study will be analyzed as described in the most recent version of the protocol (EudraCT-Number: 2017-003241-26; IND number 135622). If a future protocol amendment necessitates a substantial change to the statistical analysis of the study data, or if analysis definitions must be modified or updated, this SAP will be amended accordingly. The content of this SAP is compatible with the International Council for Harmonisation of Technical Requirements for Pharmaceuticals for Human Use (ICH)/Food and Drug Administration (FDA) E9 Guidance documents (ICH E9, 1998).

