#### **3.2.2.3 Study Entry visit**

#### **3.2.2.4 The Entry Visit (EV, Visit 1) will be done on the same day as the last visit of the parent study. End date of the Evaluation Period**

The end date of the Evaluation Period will be either EOS at Month 24 or EDV for subjects who discontinue early. If a subject does not have an EOS or EDV Visit, then the final contact date will define the end date of the Evaluation Period. At the time of a clinical cutoff prior to the study completion, if a subject is ongoing and doesn't have the EDV, the end of the Evaluation Period is set to the clinical cutoff date.

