**Table 3–3.21: Start and end of EP0093 analysis periods**

Description	Start	End	Details
Evaluation Period	Entry Visit (EV, Visit 1)	EOS or EDV or the last contact date if neither EOS or EDV visit is available.  At the time of a clinical cutoff prior to the study completion, if a subject is ongoing and doesn't have the EDV, the end of the period is set to the clinical cutoff date.	The Entry Visit (EV, Visit 1) will be done on the same day as the last visit of the parent study. Subjects will return to clinic every 2 weeks during Month 1, every month during Month 2-3, every 3 months after Month 3 up to Month 24.
Taper Period/ Safety Follow-Up Period	1 day after end date of evaluation period.	The date of final contact.  At the time of a clinical cutoff prior to the study completion, if a subject is ongoing, the end of the period is set to the clinical cutoff date.	Applies only to patients who discontinue the study or complete it without continuation of PSL treatment.
Exposure Period	Date of first dose of PSL	Date of last dose of PSL	Extends from the date of first dose until the last dose of PSL in EP0093. It may include the Evaluation and Taper Period. (Section 3.2.2.1).

At the time of a clinical cutoff prior to the study completion, subjects without the Study Termination eCRF will be classified as “ongoing.” Only the data on or prior to the clinical cutoff date will be included in the analyses.

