# 5 STUDY POPULATION CHARACTERISTICS

## 5.1 Subject disposition

Screen failure data of screened subjects who did not meet study eligibility criteria are collected on the Study Termination CRF (dates of screen failure and last contact and reason for screen failure).

Details on the last study visit are obtained from the Study Termination CRF. Variables include date of last administration of study medication, date of final contact with the subject, subject

status at study termination, date of premature study termination and primary reason for premature study termination (as listed on CRF).

The disposition of subjects will be summarized for the ES, and SS overall and by region, country as well as by investigator.

Summaries of the numbers of screened subjects and reasons for screen failures will be produced overall for the ES.

The disposition will also be presented as the number and percentage of subjects who started, completed or discontinued the study. Discontinuation of study includes a breakdown of primary reasons for discontinuation. These tables are presented overall and by region for the SS.

The number and percentage of subjects in the SS who discontinued due to AE categorized by serious fatal, non-fatal, and non-serious fatal AE incidence will also be summarized for the SS. Of note, the corresponding table is required for data transparency reporting.

Listings will be provided for disposition, reason for discontinuation and visit dates.

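### SAP 10.2.2.11 has no rule for subjects stopped by the early study termination; as the SAP reads they become discontinuation events, which lowers the later Kaplan-Meier retention estimates

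*SAP*

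**What the plan says.** SAP 10.2.2.11 plans Kaplan-Meier estimates, in the Safety Set, of the percentage of subjects completing 3, 6, 12, 18 and 24 months of treatment. It contains three rules:

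- **Event:** "For subjects who discontinued from the study, the event date is set to the date of last dose of PSL". There is no split by reason.
- **Censored:** "Subjects who completed the study will be censored as of the date of last dose of PSL in EP0093".
- **Censored:** subjects who are ongoing at a clinical cutoff, at the last-dose date defined for interim analyses.

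Early termination of the study is mentioned twice. SAP 3.9 gives it as a reason for changing protocol-defined analyses, and the rationale for Amendment 1 in SAP 14.1 names it as something to be clarified. The present Kaplan-Meier wording came in with that amendment (Change #47). Protocol 11.4 provides for such a closure: "UCB reserves the right to temporarily suspend or prematurely discontinue this study either at a single site, multiple sites, or at all sites". None of these sections says how a subject stopped by the closure enters this analysis.

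**The concern.** A subject who is still taking PSL when the sponsor closes the study has not failed on treatment. All that is known is that time on treatment would have been at least as long as observed, which is the ordinary case for right censoring. The SAP already treats a subject who is on treatment at a data cutoff this way. A subject on treatment at study closure is in the same position, but the text leads to the opposite coding.

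The landmark percentages would then mix two things: stopping for lack of effect, intolerance or personal choice, and the calendar date of closure relative to each subject's entry. A reader would take them as retention on PSL and see a figure that is too low at the later landmarks. The disposition table by primary reason would show how many subjects stopped because of closure, but it does not correct the Kaplan-Meier percentages.

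**Working it through.** **Step 1. How the documents classify a subject stopped by closure before Month 24.** No section does so directly, so the relevant texts have to be read together.

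- SAP 3.2.2.4: "The end date of the Evaluation Period will be either EOS at Month 24 or EDV for subjects who discontinue early". If neither visit exists the final contact date is used, which does not make the subject a completer.
- Protocol 8.1.7 and 8.1.8, with the schedule of assessments: the Early Discontinuation Visit is for subjects leaving early; the End of Study Visit is for completers and is placed at Month 24.
- SAP 5.1: "The disposition will also be presented as the number and percentage of subjects who started, completed or discontinued the study". There is no further category.
- SAP 3.2.3, note to the table of analysis periods: at a cutoff before study completion, "subjects without the Study Termination eCRF will be classified as" ongoing. SAP 1 describes a "detailed description of statistical methodology for the statistical analyses to support the final" clinical study report, so this category does not serve the final analysis.
- Protocol 6.3, withdrawal criterion 2: a sponsor request is a reason for withdrawal. It is written for individual subjects, not for closure of the study, but it points the same way.

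On this reading the subject is not a completer and not ongoing, and is therefore an event at last dose.

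**Step 2. Effect on the estimate.** There is no plan figure to reproduce: SAP 2.4 gives no sample size calculation, and the documents state no expected retention or dropout rate. Define:

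- S(t): the probability of still being on PSL at time t if the study had not been closed.
- A(t): the share of subjects whose time from entry to closure is at least t.

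If closure time is independent of discontinuation, censoring the sponsor stops estimates S(t), and coding them as events estimates S(t) × A(t). Since A(t) ≤ 1, event coding can never give the higher value.

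Month 12, with assumed values of S and A:

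| True S(12) | A(12) = 0.90 | A(12) = 0.75 |
|---|---|---|
| 0.90 | 0.90 × 0.90 = 0.81 | 0.90 × 0.75 = 0.675 |
| 0.80 | 0.80 × 0.90 = 0.72 | 0.80 × 0.75 = 0.60 |
| 0.60 | 0.60 × 0.90 = 0.54 | 0.60 × 0.75 = 0.45 |

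**Step 3. Simulation check.** The setting was 200,000 subjects, exponential discontinuation with 80% retained at month 12, 10% or 25% stopped uniformly between months 6 and 12, and the rest stopped uniformly between months 12 and 24. The 12-month estimate was 0.800 or 0.799 with sponsor stops censored, and 0.720 or 0.601 with them coded as events. Months 3 and 6 were identical under both codings.

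**Step 4. Pattern over the landmarks.** SAP 3.2.5 sets a month at 30 days, so months 6, 12, 18 and 24 are days 180, 360, 540 and 720. Assume 30% discontinue per 360 days, so S(t) = 0.70^(t/360), and closure times uniform over days 180 to 1080, so A(t) = (1080 − t)/900 from day 180:

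| Landmark | S(t), stops censored | A(t) | S(t) × A(t), stops as events |
|---|---|---|---|
| Month 6 | 83.7% | 1.0 | 83.7% |
| Month 12 | 70.0% | 0.8 | 56.0% |
| Month 18 | 58.6% | 0.6 | 35.1% |
| Month 24 | 49.0% | 0.4 | 19.6% |

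If closure times instead run over days 90 to 720, A(360) = 360/630 = 0.571 and month 12 reads 40.0% against 70.0%. A(720) is then 0 and month 24 reads 0%, where the honest answer is that it cannot be estimated.

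Twelve such scenarios were examined: discontinuation of 20%, 30% or 40% per 360 days, crossed with four closure patterns. The month 12 estimate fell by about 12 to 46 percentage points and the month 24 estimate by about 22 to 64 points. All of these inputs are assumptions.

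**The case against.** - **The classification rests on a form that is not shown.** Neither document defines completion of the study, and SAP 5.1 takes subject status from the Study Termination CRF. If that form codes sponsor-closed subjects as completers, they are censored and the bias disappears. This stands. It means the event status is inferred, and the text still needs to settle it, because two programmers could produce different curves from the same section.
- **The SAP may intend all-cause persistence.** A subject stopped by closure at month 9 did not complete 12 months of treatment. That is true, but with no censoring before Month 24 the estimate is just the raw proportion still on treatment. In one simulated run of 1000 subjects under the Step 4 assumptions, 565 remained at risk at day 360 and the event-coded estimate was 56.5%. A Kaplan-Meier analysis would then add nothing to the exposure table, and censoring ongoing subjects at a cutoff suggests that retention is what is wanted.
- **Independence of closure cannot be verified**, because the documents do not give the reason for termination. This stands as a caveat, and it is a good reason to keep the all-cause version as well.
- **Other tables limit the harm.** SAP 9.1 tabulates cumulative exposure at 3, 6, 9, 12, 18 and 24 months on the same last-dose clock, so a number-at-risk row would be partly redundant. These tables make a misreading less likely but leave the curve as it is.
- **The variable is minor.** SAP 2.2.2.2 lists it among the other efficacy variables, with no test and no comparator. This limits how much weight the point carries.

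**Conclusion.** The concern holds. Followed as written, and with completion meaning the Month 24 visit, SAP 10.2.2.11 codes administrative closure as failure of retention. The direction is certain: recoding censored times as events can only lower a Kaplan-Meier estimate or leave it unchanged. Landmarks that every subject could reach before closure are unaffected, for example months 3 and 6 if entry ended at least 6 months before closure.

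The size cannot be computed, because the documents do not give entry dates, the closure date or the number of subjects stopped. The illustrative month 12 losses run from 6 points (60% read as 54%) to 22.5 points (90% read as 67.5%) in the simple table, and are larger under heavier closure. They rest on assumed retention, assumed closure shares and independence of closure from outcome. No primary conclusion depends on this analysis. It should be corrected before the final analysis because the retention percentages would otherwise be misleading.

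**What to change.** Add a rule to SAP 10.2.2.11 along these lines:

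> Subjects whose primary reason for premature termination on the Study Termination CRF is termination of the study by the sponsor will be censored at the date of last dose of PSL.

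In addition:

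- Keep the all-cause version, with these subjects as events, as a sensitivity analysis.
- Report how many subjects are censored for this reason.
- Show the number at risk at 3, 6, 12, 18 and 24 months, and give no estimate where none remain at risk.

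The last-dose definition of time on treatment in SAP 10.2.1.8 stays as it is.

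The cost is one sentence, one extra run and one table row. No new data are needed, since SAP 5.1 already lists "date of premature study termination and primary reason for premature study termination (as listed on CRF") among the collected variables. The one thing to confirm first is that the CRF categories separate sponsor termination of the study from other reasons. If they do not, or if such subjects are coded as completers, the SAP should say how they are identified.

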#### **10.2.2.12 Treatment satisfaction**

A per-subject listing will be provided with all subscale scores for FAS overall.

## **11 COVID-19 IMPACT**

The impact of COVID-19 global pandemic on this study is detailed in section 3.10. COVID-19 impact will be listed by impacted visit, date, impact category, and relationship to COVID-19 (confirmed, suspected, general circumstances around COVID-19 without infection or other) in the ES. Impact of COVID-19 for any reason by country will be tabulated in the ES.

This document cannot be used to support any marketing authorization application and any extensions thereof or variations thereof.

### 13 APPENDICES

#### 13.1 LABORATORY ASSESSMENTS – PCST

The following criteria will be applied in the determination of possibly clinically significant treatment emergent laboratory assessment values.

##### 13.1.1 Hematology

PARAMETER	AGE RANGE	UNIT (conventional)	ABNORMALITY CRITERIA (conventional)	UNIT (standard)	ABNORMALITY CRITERIA (standard)
Hematocrit	<2y	%	≤27 >45	%	≤27 >45
	2y - <18y		≤29 >47		≤29 >47
	≥18y		≤85% of LLN ≥115% of ULN)		≤85% of LLN ≥115% of ULN
Hemoglobin	<2y	g/dL	≤9.0 >15.0	g/L	≤90 >150
	2y - <18y		≤9.5 >16.0		≤95 >160
	≥18y		≤85% of LLN ≥115% of ULN		≤85% of LLN ≥115% of ULN
WBC/Leukocytes	<12y	10  /L	<3.5 >15.0	G/L	<3.5 >15.0
	≥12y		<3.0 >12.0		<3.0 >12.0
Neutrophils Absolute	>1m	10  /L	<1.5	G/L	<1.5
Lymphocytes	<6m	%	≤30.0	%	≤30.0

PARAMETER	AGE RANGE	UNIT (conventional)	ABNORMALITY CRITERIA (conventional)	UNIT (standard)	ABNORMALITY CRITERIA (standard)
	6m - <6y		≤22.0		≤22.0
	6y - <18y		≤12.0 ≥80.0		≤12.0 ≥80.0
	≥18y		≤10.0 ≥80.0		≤10.0 ≥80.0
Basophils	>1m	%	≥3.0	%	≥3.0
Eosinophils	>1m	%	≥10.0	%	≥10.0
Monocytes	>1m	%	≥20.0	%	≥20.0
Platelets	>1m	10  /L	≤100 ≥600	G/L	≤100 >600
RBC/ Erythrocytes	<2y	10  /L	<3.0	T/L	<3.0
	≥2y		<3.5		<3.5

Abbreviations: F=female; M=male; m=month; y= year. A month is defined as 30 days; a year is defined as 365.25 days.

**13.1.2 Blood chemistry**

PARAMETER	AGE RANGE	UNIT (conventional)	ABNORMALITY CRITERIA	UNIT (standard)	ABNORMALITY CRITERIA
AST (SGOT)	<14y	U/L	>180	U/L	>180
	≥14y		>144		>144
ALT (SGPT)	1y - <18y	U/L	>90	U/L	>90
	≥18y		>123		>123
Alkaline Phosphatase	<4y	U/L	>690	U/L	>690
	4y - <10y		>834		>834
	10y - <18y		>1174		>1174
	≥18y		>432 (F)		>432 (F)
GGT	<6m	U/L	>522	U/L	>522
	6m - <1y		>279		>279
	1y - <13y		>66		>66
	13y - <18y		>126		>126
	≥18y		>255		>255
Total Bilirubin	>1m	mg/dL	≥1.5	umol/L	≥25.656

PARAMETER	AGE RANGE	UNIT (conventional)	ABNORMALITY CRITERIA	UNIT (standard)	ABNORMALITY CRITERIA
Total Protein	2m-<1y	g/dL	<3.0	g/L	<30
	≥1y		<4.3		<43
Albumin	<1y	g/dL	<1.6	g/L	<16
	≥1y		<2.4		<24
BUN	<1y	mg/dL	>21	mmol/L	>7.497
	≥1y		>30		>10.71
Urea	<1y	mg/dL	>42	mmol/L	>7.014
	≥1y		>60		>10.02
Creatinine	1y - <10y	mg/dL	>0.9	umol/L	>79.56
	10y - <16y		>1.4		>123.76
	≥16y		>1.6		>141.44
Creatinine Clearance*	All	mL/min	<70	mL/s	<1.169
Calcium	<1y	mg/dL	<6.9	mmol/L	<1.725
	1y - <18y		<7.4		<1.85
	≥18y		<7.9 >11.1		≤1.975

PARAMETER	AGE RANGE	UNIT (conventional)	ABNORMALITY CRITERIA	UNIT (standard)	ABNORMALITY CRITERIA
Phosphorous	<1y	mg/dL	<1.8	mmol/L	<0.5814
	≥1y		<1.8		<0.5814
Potassium	<1y	mEq/L	<3.0	mmol/L	<3.0
	≥1y		<3.0		<3.0
Sodium	>1m	mEq/L	≤130	mmol/L	≤130
Glucose	>1m	mg/dL	<50	mmol/L	<2.775
Total Cholesterol	1y - <18y	mg/dL	>250	mmol/L	>6.475
	≥18y		>300		>7.77
LDL (calculated)	1y - <18y	mg/dL	>140	mmol/L	>3.626
	≥18y		>200		>5.18
HDL	≤2y	mg/dL	<10	mmol/L	<0.259
	>2y		<20		<0.518
Triglycerides	<1y	mg/dL	>750	mmol/L	>8.475
	≥1y		>250		>2.825

PARAMETER	AGE RANGE	UNIT (conventional)	ABNORMALITY CRITERIA (conventional)	UNIT (standard)	ABNORMALITY CRITERIA (standard)
Uric Acid	<1y	mg/dL	>7.7	umol/L	>457.996
	1y - <13y		>6.5		>386.62
	13y - <18y		>8.6		>511.528
	≥18y		>6.8 (F) >9.6 (M)		>404.464 (F) >571.008 (M)
Thyroxine (T4)	<1y	ug/dL	≤4.3 ≥18.4	nmol/L	≤55.3453 ≥236.8264
	≥1y		≤3.8 ≥13.5		≤48.9098 ≥173.7585
Globulin	<1y	g/dL	<1.0 >3.8	g/L	<10 >38
	≥1y		<1.2 >4.4		<12 >44

Abbreviations: ALT= alanine aminotransferase; AST = aspartate aminotransferase; BUN = blood urea nitrogen; dL = deciliter; F=female; GGT: gamma-glutamyltransferase; HDL = high density lipoprotein; LDL = low density lipoprotein; L = liter; M=male; m = month (a month is defined as 30 days) mg = milligram; mmol = millimoles; µg = microgram; U = unit; ULN = upper limit of normal; y = years (a year is defined as 365.25 days). \*Schwartz equation (patients <12): Cr Cl ml/min = [Height (cm) \* 0.55] / serum creatinine Cockcroft equation (patients >12): Male: Cr Cl ml/min = [(140-age) x body weight (kg)] / (72 x serum creatinine); Female: Cr Cl ml/min = [(140-age) x body weight (kg)] / (72 x serum creatinine) x 0.85

### 13.1.3 Urinalysis

Qualitative urine parameters are generally reported by a descriptive score, which differs among laboratories. For data analysis purpose, a four-point scale is used. Five-point, six- point, or seven-point scales will be collapsed into a four-point scale first. A value is considered possibly clinically significant treatment emergent abnormal if an upward shift of at least 2 degrees from the baseline occurs under investigational treatment. To collapse the results in a five-point scale into a four-point scale, the lowest two positive results will be combined (see example below). For results reported with a scale of more than five-point, please consult your study physician for how to collapse into four-point scale.

Original Five-point Scale	Four-point Scale
Negative/None	Negative/None
Trace/Rare/Mild/A Few	Trace/1+/Rare/Mild/A Few
1+	
2+/Mod	2+/Mod
3+/Sev	3+/Sev

This document cannot be used to support any marketing authorization application and any extensions or variations thereof.  
 REDACTED COPY

### 13.2 VITAL SIGN ASSESSMENTS - ABNORMAL

Abnormality criteria to be applied in the assessment of vital signs parameter values are given below.

PARAMETER	AGE RANGE	ABNORMALITY CRITERIA
Pulse Rate (beats/minute)	<6m	<100 >180
	6m - <3y	<90 >150
	3y - <12y	<60 >130
	12y - <17y	<50 >120
	≥17y	<50 and a decrease from Baseline of ≥15 >120 and an increase from Baseline of ≥15
Systolic Blood Pressure (mmHg)	<6m	<60 >100
	6m - <3y	<70 >120
	3y - <12y	<80 >140
	12y - <17y	<90 >160
	≥17y	≤ 90 and a decrease from Baseline of ≥20 ≥ 180 and an increase from Baseline of ≥20
Diastolic Blood Pressure (mmHg)	<6m	<40 >65
	6m - <3y	<45 >75
	3y - <12y	<50 >80
	12y - <17y	<50 >105
	≥17y	<50 and a decrease from Baseline of ≥15 >105 and an increase from Baseline of ≥ 15
Respiratory Rate (breaths/minute)	<6m	<25 >55
	6m - <3y	<20 >45
	3y - <12y	<15 >35
	≥12y	<10 >25
Body Weight	1m - <17y	<3% or 97% of the normal body weight growth curve ranges based on gender and the age of subject on date of weight assessment a

---

PARAMETER	AGE RANGE	ABNORMALITY CRITERIA
	≥17y	≥ 10% change from Baseline (an increase or a decrease) a

Abbreviations: m = month, y = year. A month is defined as 30 days; a year is defined as 365.25 days.

asource: <http://www.cdc.gov/growthcharts/>

This document cannot be used to support any marketing authorization application and any extensions or variations thereof.

REDACTED COPY

### 13.3 ELECTROCARDIOGRAM (ECG) – ABNORMAL

Abnormality criteria to be applied in the assessment of ECG parameter values are given below:

Parameter	Age	Abnormality Criteria
QT interval (ms)	1m-<12y	>500
	>12y	>500 or ≥60ms increase from Baseline
QTc(F) (ms)	<6m	>490, or >15% increase from Baseline
	6m-<3y	>440, or >15% increase from Baseline
	3y-<12y	>440, or >15% increase from Baseline
	>12y- <17y	>440, or >15% increase from Baseline
	≥17y	>500 or ≥60ms increase from Baseline
QTc(B) (ms)	<6m	>490, or >15% increase from Baseline
	6m-<3y	>450, or >15% increase from Baseline
	3m-<12y	>450, or >15% increase from Baseline
	>12y- <17y	>450, or >15% increase from Baseline
	≥17y	>500 or ≥60ms increase from Baseline
PR interval (ms)	<6m	>150, or >25% increase from Baseline
	6m-<3y	>170, or >25% increase from Baseline
	3y-<12y	>180, or >25% increase from Baseline
	>12y - <17y	>200, or >25% increase from Baseline
	≥17y	Treatment-emergent value >200, >220, >250
QRS interval (ms)	<6m	>90, or >25% increase from Baseline
	6m-<3y	>90, or >25% increase from Baseline
	3y-<12y	>100, or >25% increase from Baseline
	>12y - <17y	>110, or >25% increase from Baseline
	≥17y	Treatment-emergent value >100, >120, >140
Heart rate (bpm)	<6m	<100, >180
	6m-<3y	<90, >150
	3y-<12y	<60, >130
	>12y	<50, >120

Abbreviations: bpm = beats per minute; m = months; ms = milliseconds; QTc = corrected QT interval; y = years. A month is defined as 30 days; a year is defined as 365.25 days.

Note: Treatment-emergent is defined as meeting the criteria at any post-Baseline visit during EP0093 (including unscheduled visits) and not meeting the same criteria during Baseline in the parent study.

